9.3.1.3 Bioanalytical method

Concentrations of SAR407899 in plasma samples will be measured using a validated liquid chromatography method coupled with tandem mass spectrometry (LC-MS/MS) with a lower limit of quantification of 1 ng/mL (DOH1425) under the responsibility of Covance Laboratories.

9.3.1.4 Pharmacokinetics parameters

Observed SAR407899 concentrations will be reported in the clinical study report. A population pharmacokinetic analysis may be conducted and will be reported in a separated report.

9.3.2 Pharmacogenetic assessment

9.3.2.1 Drug metabolizing enzymes DNA sample

Not applicable.

9.3.2.2 Optional stored DNA sample

For those patients who signed the optional pharmacogenetic informed consent form, a blood sample will be collected at the study visit as specified in the study flow chart and this sample will be stored for up to 15 years after completion of the final study report of the main clinical trial.

This sample may be used to determine a possible relationship between genes and response to treatment with SAR407899, how the body processes SAR407899, and possible side effects to SAR407899. Genes that may be studied include those related to ROCK pathway and/or endothelial dysfunction. This blood sample will be transferred to a site that will, on behalf of Sanofi, extract DNA from the sample and that is managed by Covance.

This blood sample, and the DNA that is extracted from it, will be assigned a second number, a genetic ID (deidentification code) that is different from the patient ID. This “double coding” is performed to separate a subject’s medical information and DNA data.

The clinical study data (coded by subject ID) will be stored in the clinical data management system (CDMS), which is a distinct database in a separate environment from the database containing the pharmacogenetic data (coded by genetic ID). The key linking subject ID and genetic ID will be maintained by a third party, under appropriate access control. The matching of clinical data and pharmacogenetic data, for the purpose of data analysis, will be possible only by using this key, which will be under strict access control. All data will be reported only in coded form in order to maintain confidentiality.

The DNA will be stored for up to 15 years from the completion of the clinical study report.

Special procedures for storage and shipping of pharmacogenetic samples are described in a separate laboratory manual and in [Appendix B](#).

[REDACTED]

9.4.1 Sampling / handling procedures

Table 1 - Summary of sampling/handling procedures for [REDACTED]

Sample volume	10 mL blood
Matrix	Serum
Anticoagulant	None
Handling procedures	See laboratory manual
Aliquot split	4 aliquots with 1 mL serum for the first three aliquots, at each timepoint
Storage conditions	-20°C
Shipment conditions	In dry ice

Table 2 - Summary of sampling/handling procedures for [REDACTED]

Sample volume	10 mL blood
Matrix	Serum
Anticoagulant	None
Handling procedures	See laboratory manual
Aliquot split	4 aliquots with 1 mL serum for the first three aliquots, at each timepoint
Storage conditions	-20°C
Shipment conditions	In dry ice

Special procedures for collection, storage and shipping of blood/plasma/serum will be described in a separate laboratory manual.

9.4.2 Biomarker assay methods

The methods are still under development. Methods will be described in a separate laboratory manual.

9.5 FUTURE USE OF SAMPLES FOR BIOMARKER SAMPLES

Table 3 - Summary of sampling/handling procedures for future use of samples

Sample volume	4 mL blood
Matrix	Serum
Anticoagulant	None
Handling procedures	See laboratory manual
Aliquot split	8 aliquot of 0.250 mL serum at each timepoint
Storage conditions	-20°C
Shipment conditions	In dry ice

For patients who have consented to it, one sample will be collected at the visits specified in the study flow chart and these samples will be stored for up to 15 years after completion of the final study report. These samples may be used for other research purposes (excluding genetic analysis) related to endothelial dysfunction and/or microvascular angina.

These other research analyses will help to understand either disease subtypes or drug response, or to develop and/or validate a bioassay method, or to identify new drug targets or biomarkers.

[figure not shown]
These samples will remain labelled with the same identifiers than the one used during the study (ie, subject ID). They will be transferred to a Sanofi site (or a subcontractor site) which can be located outside of the country where the study is conducted. The Sponsor has included safeguards for protecting subject confidentiality and personal data.

Special procedures for storage and shipping are described in a separate laboratory manual.

9.6 SAMPLE BLOOD VOLUME

Sample blood volume is presented in the table below.

Table 4 - Sampled blood volume

Type	Volume per sample	Sample number	Total
Laboratory	5 mL	7	35 mL
	10 mL	1	10 mL
	10 mL	1	10 mL
Future use of sample	2.5 mL	1	2.5 mL
Pharmacogenetics	6 mL	1	6 mL
Pharmacokinetics	2 mL	7	14 mL
Total for male patient			Approximately up to 80 mL
FSH	10 mL	1	10 mL
Total for female patient			Approximately up to 90 mL

9.7 APPROPRIATENESS OF MEASUREMENTS

Please refer to [Section 4](#).

Primary endpoint:

Change from baseline to end of study treatment/Week 4, in uncorrected global CFR assessed by ¹³N-ammonia or ⁸²Rubidium PET scan will be the primary endpoint as CFR represents the increase in blood flow to the myocardium in response to metabolic or pharmacological stimulations, the critical factor in angina. CFR is the endpoint with the most abundant clinical data in MVA patients. An abnormal CFR is <2.0.

The standard deviation and the mean of the placebo group of a study published by (1), using a noninvasive measures of coronary flow reserve based on rest/stress PET in 2783 patients with known or suspected coronary artery disease, were used in sample size calculation.

Secondary endpoints:

Change from baseline to end of study treatment/Week 4 in physical limitation as assessed by the SAQ-PL will be the secondary endpoint as it relates to patients' physical activity. The Seattle Angina Questionnaire (SAQ) is widely used to understand patients' perceptions of cardiovascular disease and symptoms. It was used in pilot MVA studies. Although data will be collected on multiple dimensions of the SAQ, the physical limitation (PL) dimension is the most relevant for defining treatment benefit in this population.

SAR407899 peak and trough concentrations will also be assessed as secondary endpoint as no data on microvascular angina patient and/or persistent stable angina despite angiographically successful PCI population are available with this compound.

10 STUDY PROCEDURES

10.1 VISIT SCHEDULE

10.1.1 Visit 0: Screening visit

The screening visit has to be performed 4 weeks to one day before scheduled (first) dosing (Day 1) and up to 6 weeks in patients before scheduled (first) dosing with CCTA during screening.

Informed Consent

Information on the study will be given to and discussed with the patient. The patient will sign the informed consent for the current trial before any procedure. When the consent has been obtained, full identification of patient and personal physician will be recorded for the Investigator's record, and a subject number will be assigned as described in [Section 8.3](#).

Also the informed consents have to be obtained for the optional DNA banking and future use of samples for possible later further analyses.

Collection of adverse events has to be started from the time of signing informed consent. The patient has to be registered with the IVRS/IWRS.

After the informed consent has been signed, the following measurements have to be performed:

- Call IVRS/IWRS to assign patient number.
- Demographic information.
- Collection of prior/concomitant medications.
- Begin AEs reporting.
- Medical/surgical history.
- Data of previous (if done 24 months prior to screening) coronary artery angiography or CCTA.
- Data of previous (if done between 24 months and 5 years prior to screening) coronary artery angiography or CCTA.
- Data of previous (if done 24 months prior to screening) CFR assessment whatever the method.
- Assessment of inclusion and exclusion criteria.
- Physical examination (including smoking habits).
- Body weight and height.
- Vital signs, resting 12 lead-ECG.

Patients who do not meet inclusion criteria and/or met at least one exclusion criterion will be considered a screening failure and will not perform the following measurements:

- Blood sampling for hematology, biochemistry and plasma FSH (For post-menopausal female patients not treated with HRT).
- Blood sampling for renal function (blood creatinine and cystatin C).
- Collection of urine for urinalysis.
- A patient diary will be dispensed to the eligible patients in order to record their angina episodes and the short-acting nitrates intakes.
- Patients who meet all the inclusion criteria and none of the exclusion will be potentially eligible for inclusion into the study depending on PET scan CFR value assessed at baseline visit or if not otherwise possible up to 14 days prior to Day 1 (except for patients described below where PET scan will be performed up to 4 weeks prior to Day 1). A visit within the next 4 weeks will be scheduled.

In patients diagnosed with MVA and stable angina without previous PCI, who did not have coronary angiogram or CCTA in the previous 24 months but within 5 years, a CCTA will be performed during screening period provided that:

- These patients meet all inclusion criteria including qualifying PET scan and $CFR < 2.0$ up to 4 weeks before Day 1 visit. If not, the patient will be screen failed and will not have CCTA.

The Investigator will call the patient to confirm the date for CCTA, to be performed in order to have the results before Day 1 visit to ascertain the absence of obstructive coronary arteries.

At the end of the screening visit, the patient should be informed and follow restriction rules for PET scan investigation: methylxanthines (eg, caffeine) will be forbidden 24 hours prior to the test otherwise PET scan should be re-scheduled one day after. All site visits whereby the PET assessment is not performed on the same day as the site visit will not require fasting or other dietary / medication restrictions.

Screening failure

If the patient is not eligible after this visit and after all reports are available, this information has to be entered into the IVRS/IWRS by a screening failure call.

In case the PET scan cannot be performed in the allowed time window for logistical reasons, the patient can be re-screened after consultation with the sponsor.

10.1.2 Visit 1: Baseline / Randomization / Day 1

The patient has to go on Day 1 morning to the investigational site for his / her visit.

Patients diagnosed with MVA and stable angina without PCI, who did not have a coronary angiogram or CCTA in the previous 24 months but between 24 months to 5 years, need to have

the PET assessment followed by the CCTA during the screening period. Other patients will have their PET scan up to 14 days before Day 1 visit or on Day 1 visit.

For the PET assessment, the patient should be in fasting state (at least 4 hours) and well hydrated and should avoid, in the following timely manner (whenever possible), the intake of:

- 24 hours before CFR assessment :
 - Anti-hypertensive drugs,
 - Beta blockers,
 - Calcium channel blockers,
 - Methylxanthines including caffeinated coffee, tea or other caffeinated beverages, caffeine-containing drug products.
- At least 4 hours before CFR assessment:
 - Nicotine,
 - Short acting nitrate.

If not, this visit should be re-scheduled one day after with the restrictions re-explained to the patient.

The following assessments are to be completed at Day 1 as follows:

- Quality of life questionnaires should be filled in prior any other assessment and without any help:
 - Seattle Angina Questionnaire,
 - Patients' perceptions of treatment and symptoms.
- Resources utilization.

Prior any IMP administration, the following assessments will be performed:

- Assessment of part of inclusion and exclusion criteria.
- Physical examination (including smoking habits).
- Patient diary evaluation: angina episodes with severity (intake of short-acting nitrate).
- Body weight.
- Body temperature.
- DNA blood sample (provided appropriate consent has been obtained).
- [REDACTED]
- Blood sampling for future use of samples (provided appropriate consent has been obtained).
- Blood sampling for renal function (blood creatinine and cystatin C).
- Blood sampling for hematology, biochemistry.

- Collection of urine for urinalysis.
- Vital signs including orthostatic BP measurements and resting 12 lead-ECG.
- Coronary Flow Reserve assessed by vasodilator stress PET scan with NIMPs administration (can be performed up to 14 days prior to Day 1).
- AEs collection.
- Concomitant treatments reporting.

One hour before dosing, a standard meal can be given to the patient.

Just before the study drug administration, 12 lead-ECG and vital signs assessments will be performed (only if PET scan is done at Day 1 or according to creatinine results availability if PET scan done prior to Day 1).

If the patient is still eligible after all assessments, the investigator or designee will call the IVRS/IWRS to randomize the patient and obtain a treatment number assigned by IVRS/IWRS.

If the patient is not eligible after these assessments, this information has to be entered into the IVRS/IWRS by a screening failure call.

Then the 1st IMP intake has to be given on Day 1.

After dosing the following assessments have to be performed according to the period flow chart (see at [Section 1.4](#)):

- Evaluation of AEs and concomitant medication.
- Vital signs at T1h and T3h post IMP intake.
- Resting 12 lead ECG.
- Collection of PK sample (T1h and T3h).

If no clinically relevant findings have been detected from all safety examinations until then, the patient can leave the unit in the evening or earlier depending on the investigator's judgment of Day 1.

Day 1 discharge time:

- Before the patient leave the unit, he/she will be given sufficient study drug (packaged in a Wallet) for 1 treatment week (± 2 days).
- At home, the patient will take the IMP twice a day (morning and bedtime) and will report on his patient diary IMP information and the angina episodes that will occur and short-acting nitrate intakes.
- In case a patient does not tolerate a dose, he/she should call the investigator to have an on-site visit. Based on the tolerability assessed at this visit, the investigator could decide to stop or modify study drug dose (the IVRS/IWRS will be called in that cases).

10.1.3 Visits 2, 3, and 4: Days 8, 15, and 22 (+/- 2 days)

During the titration phase, patient's visits are performed at the clinical site. The following assessments have to be performed before the administration:

- Physical examination may be symptoms driven at the investigator's discretion.
- Collection of information about concomitant medication/concomitant treatment reporting.
- AEs collection.
- Vital signs (BP & heart rate measurements including search of hypotension) and resting 12 lead-ECG before study drug administration.
- Collection for PK samples (pre-dose).
- Collection for renal function (blood creatinine and cystatin C).
- Collection for hematology (except at D15 and D22), biochemistry.
- Patient diary (one per week) review & dispensation.
- Call IVRS/IWRS to obtain the treatment kit code after specifying the chosen titration.
- After these assessments, the IMP morning administration could be done.
- In case a patient does not tolerate a dose, he/she should call the investigator to have an on-site visit. Based on the tolerability assessed at this visit, the investigator could decide to stop or modify study drug dose.
- Before the patient leave the unit, he/she will be given sufficient study drug (packaged in a Wallet) for 1 treatment week (± 2 days).
- At home, the patient will take the IMP twice a day (morning and bedtime) and will report on his patient diary IMP information and the angina episodes that will occur and short-acting nitroglycerin intakes.

10.1.4 Visit 5: End of treatment: Day 29 (or up to 2 days after at the latest) even in case of early IMP discontinuation

The patient arrives to the clinical site in the morning on Day 29 (or up to 2 days after at the latest) and should be in fasting state (at least 4 hours) and well hydrated and should avoid, in the following timely manner (whenever possible), the intake of as it relates to the PET assessment:

- 24 hours before CFR assessment :
 - Anti-hypertensive drugs,
 - Beta blockers,
 - Calcium channel blockers,
 - Methylxanthines including caffeinated coffee, tea or other caffeinated beverages, caffeine-containing drug products.
- At least 4 hours before CFR assessment :
 - Nicotine,

- Short acting nitrate.

IMP administration should be continued until the visit to the site.

The following assessments have to be performed:

- Quality of life questionnaires should be filled in prior any other assessment and without any help:
 - Seattle Angina Questionnaire,
 - Patients' perceptions of treatment and symptoms.
- Physical examination (including smoking habits).
- Patient diary collection.
- Body weight.
- Body temperature.
- Vital signs including search of orthostatic BP measurements and resting 12 lead-ECG.
- Blood sampling for renal function (blood creatinine and cystatin C).
- Blood sampling for hematology, biochemistry.
- Collection of urine for urinalysis.
- Collection of PK samples (pre-dose).
- AEs collection.
- Collection of information about any concomitant medications.

After IMP intake:

- Coronary flow reserve assessed by vasodilator stress PET scan with NIMPs administration, is performed approximately 1 to 2 hours after IMP intake.
- Collection of PK samples (1-3h post-dose).
- Call IVRS/IWRS to declare the end of treatment for this patient, except if patient has delay in end-of-treatment PET scan.

If no clinically relevant findings have been detected from all safety examinations until then, the patient can be discharged from the unit in the evening or earlier depending of the investigator's judgment.

Approximately seven days after the last study drug intake, the investigator will prescribe if needed anti-anginal drugs (ie, nitrates) and/or PDE 5 inhibitor.

Only if PET scan performed after Day 29 visit, at home, the patient will take the IMP twice a day (morning and bedtime) and will report on his patient diary IMP information and the angina episodes that will occur and short-acting nitroglycerin intakes.

In case of early IMP discontinuation:

- Within the first 2 weeks of study treatment patients are to be assessed as soon as possible after study drug stop, using the procedures (except PET scan) planned for the D29/end of treatment visit, including a pharmacokinetic sample (to be collected no later than 3 days after the last study drug intake).
- With at least 2 weeks of study treatment patients are to be assessed as soon as possible after study drug stop, using the procedures planned for the D29/end of treatment visit, including a pharmacokinetic sample (to be collected no later than 3 days after the last study drug intake). PET scan can be performed up to 3 days after study drug discontinuation.

10.1.5 Visit 6: End of study: Day 36 (+/- 2 days)

Visit at clinical site:

- Patient's diary review.
- Vital signs (BP & heart rate measurements including search of hypotension) and resting 12 lead ECG.
- Blood sampling for hematology, biochemistry.
- Blood sampling for renal function (blood creatinine and cystatin C).
- AEs collection.
- Collection of information about any concomitant medications.

Study restriction(s)

There is no restriction of meals with regard to contents or time schedule.

This visit is not mandatory in case of premature treatment discontinuation.

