- c Concomitant medication (if those are not allowed during the study, see exclusion criterion 3 in [Section 7.2.1](#)) needs to be stopped 1 week before baseline CFR assessed by PET scan and during the whole study.
- d Capsules in the morning and at bedtime. If PET assessment on Day 29 no administration at bedtime. If PET assessment delayed, last IMP administration should be done in the morning of the PET assessment.
- e Vital signs: BP & heart rate measurements including search of hypotension (orthostatic or not).
- f Before morning administration, vital signs should be assessed by the investigator or designee except on Day 1 which requires before morning administration, at T1H and T3H. For any safety reasons additional physical examination, vital signs, ECG may be performed at the investigator's discretion.
- g At Day 1 & Day 29 PET assessments, continuous monitoring of heart rate, BP and ECG should be performed throughout the stressor infusion.
- h Restriction rules for CFR assessed by vasodilator stress PET scan (detailed in [Section 10.1.2](#) and [Section 10.1.4](#)) to follow.
- i On Day 1 (or, if not otherwise possible, up to 14 days prior to Day 1) CFR assessed by vasodilator stress PET scan should be performed before the IMP administration. On Day 29 or up to 2 days after (if not otherwise possible) CFR assessed by vasodilator stress PET scan should be performed approximately 1 to 2 hours after morning IMP intake. Prior to baseline PET assessment (on day 1 or up to 14 days prior to day 1), the eligibility criteria must be carefully reviewed (including review of the screening labs), and if the patient no longer qualifies for the study, then he/she should not undergo the PET assessment.
- j To be completed before any other assessment and without any help.

- k Health care resources will include number of out-patients visits by type physician (specialists, general practitioner, other) and impact on working status.
- l Two PK samplings on Day 1 (1h and 3 h post-dose), one PK sampling (pre-dose) at Day 8, Day 15 and Day 22, two PK samplings on Day 29 (pre-dose and 1-3 hours post-dose). The patient will have to come at the site without having taken his morning dose of IMP if the visit occurs in the morning.
- m Only in post-menopausal female patient not receiving hormone replacement therapy.
- n Except hematology.
- o To assign patient number.
- p To obtain the treatment number after specifying the chosen titration.

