- Overall, the exposure to the study drug should last for 4 weeks in total (3 weeks for the titration phase and 1 week for the maintenance phase) for all patients. Patients will be followed one week after the end of the study treatment to collect any potential AEs during the washout period.
- Serum creatinine will be monitored. Creatinine is filtered in glomerulus and also partly eliminated in urine via an active secretion mediated by organic cation transporter-2 (OCT2). These observed increases in adults could then possibly be explained by inhibition of its active secretion by SAR407899 which is a weak in vitro OCT2 inhibitor. Serum cystatin C, which is filtered in glomerulus but not subject to tubular secretion, will be measured in parallel to serum creatinine to assess glomerular filtration rate.

Specific parameters rationale

Primary endpoint:

- **Coronary flow reserve (CFR)**, represents blood flow to the myocardium; the critical factor in angina. It is the endpoint with the most abundant clinical data in MVA patients. CFR is the ratio of the maximal myocardial blood flow (MBF) after a hyperemic stimulus (such as intravenous adenosine injection) to baseline resting blood flow. In patients with

normal endothelial function, adenosine increases MBF by a factor of 2.5 or more while in patients with endothelial dysfunction the increase is less than 2.0 (27).

Secondary endpoints:

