8 STUDY TREATMENTS

8.1 INVESTIGATIONAL MEDICINAL PRODUCT(S) / NON INVESTIGATIONAL MEDICINAL PRODUCT(S)

8.1.1 INVESTIGATIONAL MEDICINAL PRODUCT(S)

Investigational medicinal products:

- SAR407899, 2.5 mg and 5 mg capsules.
- SAR407899 matching placebo.

Formulation: Capsules.

Route and method of administration: Oral administration, twice per day, in the morning and at bedtime, with or without a meal.

Dose regimen: 2 capsules in the morning and at bedtime. Dose may be taken with or without food as per preference of the patient.

Starting dose: [REDACTED].

[REDACTED]

- [REDACTED]
- [REDACTED]
- [REDACTED]
- [REDACTED]

Stopping criterion based on creatinine level:

- Stop study drug if creatinine level >150 µmol/L and increase from baseline >30%. In specific circumstances where creatinine blood level can be obtained only in the afternoon the day of the visit, the patient will be titrated according to titration scheme and if creatinine blood level meets stopping rules, the investigator will need to contact the patient before bedtime intake to permanently discontinue the study drug and schedule a premature study drug discontinuation visit.

[REDACTED]

When 19 patients will have completed first week of treatment, the DMC will review the clinical safety data. During the safety evaluation of the first 19 enrolled patients, these patients will continue to receive IMPs as per the titration schedule described above and enrolment will continue.

Dosing of SAR407899 is limited to 31 days.

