9.2 SAFETY ENDPOINTS

9.2.1 Adverse events

Refer to [Section 10.4](#) to [Section 10.7](#) for details.

Adverse events, serious adverse events, and adverse events of special interest: spontaneously reported to the Investigator (see [Section 10.4](#)) will be collected from signed informed consent until the End of Study at Day 36.

To ensure the continuing safety of patients in this study, an independent DMC will be responsible for reviewing the safety data on a periodic basis throughout the course of the study as outlined in [Section 6.4.1](#).

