11.4.3 Analyses of safety data

The summary of safety results will be presented by treatment group on the basis of the safety population.

All safety analyses will be performed on the safety population using the following common rules:

- The baseline value is defined generally as the last available value before randomization.
- The analysis of the safety variables will be essentially descriptive and no hypothesis testing is planned.

The following definitions will be applied to laboratory parameters, vital signs and ECG.

- The potentially clinically significant abnormality (PCSA) values are defined as abnormal values considered medically important by the Sponsor according to predefined criteria/thresholds based on literature review and defined by the Sponsor for clinical laboratory tests, vital signs, and ECG.

PCSA criteria will determine which patients had at least 1 PCSA during the TEAE period, taking into account all evaluations performed during the TEAE period, including unscheduled or repeated evaluations. The number of all such patients will be the numerator for the PCSA percentage.

Observation period

- The TEAE observation period is defined as the time from the first dose of IMP up to 7 days after the last dose of IMP.
- The on-study period is defined as the time from randomization until the end of the study (see definition in [Section 6.2.1](#)).

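### For patients who complete treatment, the last visit and the end of adverse event collection are fixed to Day 36 (+/- 2 days) although the last dose can fall on Day 29, 30 or 31, so a compliant visit can come only 3 to 6 days after dosing, short of the protocol's own 7

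*Protocol*

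**What the plan says.** **Last dose.** Footnote i of flow chart 1.3.1 says: "On Day 29 or up to 2 days after (if not otherwise possible) CFR assessed by vasodilator stress PET scan should be performed". Footnote d adds: "If PET assessment delayed, last IMP administration should be done in the morning of the PET assessment". Flow chart 1.3.2 carries the same two rules. Section 10.1.4 has the patient keep dosing at home until a delayed scan, and footnote q provides extra supply for a scan on Day 30 or 31. Section 8.1.1 states: "Dosing of SAR407899 is limited to 31 days". A last dose on Day 29, 30 or 31 is therefore planned conduct, not a deviation.

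**Last visit.** The heading of 10.1.5 is "End of study: Day 36 (+/- 2 days", and flow chart 1.3.1 gives the same day and window. Under 9.2.1, adverse events "will be collected from signed informed consent until the End of Study at Day 36".

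**Length of follow-up.** Section 4.4 says: "Patients will be followed one week after the end of the study treatment to collect any potential AEs during the washout period". Section 6.2.1 lists one week of follow-up. Section 11.4.3 defines the treatment-emergent adverse event (TEAE) period as "the time from the first dose of IMP up to 7 days after the last dose of IMP" and counts potentially clinically significant abnormalities (PCSAs) over the same period. The synopsis derives the 7 days as five half-lives at 31 h, the conservative end of a 20 to 31 h range that depends on age.

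No section moves Visit 6 when the last dose is late.

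**The concern.** Two clocks are in use. Visit 6 and the close of AE collection run from Day 1; the follow-up promise and the TEAE/PCSA window run from the last dose. They agree for a Day 29 last dose with a visit on or after Day 36. Elsewhere a visit inside its permitted window can come before the safety window closes, with no later visit or call scheduled.

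What is at stake is the tail of the safety record. Hypotension and orthostatic hypotension are the identified risks. Under 10.4.1.3 a sufficiently large orthostatic fall is an event of special interest even without symptoms, so finding one depends on a measurement. Visit 6 carries the only scheduled blood pressure, creatinine and cystatin C checks after treatment ends. TEAE and PCSA incidence are also among the outputs that the SAP keeps (section 1.2, Table 1) after dropping the efficacy models.

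**Working it through.** **Inputs**
- Last dose, L: Day 29, 30 or 31 (1.3.1 footnotes d and i; 8.1.1; 10.1.4).
- Visit 6, V: Day 34 to 38 (10.1.5, Day 36 +/- 2).
- Required follow-up: 7 days (4.4, 6.2.1, 11.4.3).
- Half-life, h: 20 to 31 hours, with 31 used for all patients (synopsis, safety analysis).

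**The plan's own figure.** 5 x 31 h = 155 h, and 155 / 24 = 6.46 days, which the synopsis gives as approximately 7. Day 29 + 7 = Day 36. The nominal schedule reproduces.

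**Follow-up = V - L, in days**

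| Last dose | Day 34 | Day 35 | Day 36 | Day 37 | Day 38 | Visit days short of 7 |
|---|---|---|---|---|---|---|
| Day 29 | 5 | 6 | 7 | 8 | 9 | 34-35 |
| Day 30 | 4 | 5 | 6 | 7 | 8 | 34-36 |
| Day 31 | 3 | 4 | 5 | 6 | 7 | 34-37 |

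Six days is 144 h, so every short visit also misses 155 h, though at six days by only 11 h. An on-time Day 29 scan is affected as well if the visit uses the early side of its window.

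**Drug remaining = 0.5^(hours / h).** This assumes a single half-life and whole 24-hour days, and is illustrative.

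| Last dose and visit | Hours | h = 31 | h = 20 |
|---|---|---|---|
| Day 31, Day 34 | 72 | 2.3 half-lives, 20% | 3.6 half-lives, 8% |
| Day 31, Day 36 | 120 | 3.9 half-lives, 7% | 6.0 half-lives, 2% |
| Day 29, Day 34 | 120 | 3.9 half-lives, 7% | 6.0 half-lives, 2% |

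The planned five half-lives leave 0.5^5, about 3%.

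**Part of the 7-day window left unobserved.** With a Day 31 last dose, 7 - 3 = 4 days for a Day 34 visit and 7 - 5 = 2 days for a Day 36 visit.

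**The case against.** The best defence is that all the sections can be met together. Day 31 + 7 = Day 38 lies inside the permitted window, so a site that reads 4.4 and 6.2.1 alongside 10.1.5 can give every completer a full week. Section 10.3.4 also describes the Day 36 visit as coming one week after end of treatment, which shows the intent. This stands against any reading that the schedule prevents 7 days. It does not remove the point: 10.3.4 deals with withdrawals and still names D36, and nothing tells a site that the early visit days are unavailable after a late scan.

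The size can also be overread.
- A scan after Day 29 is allowed only when Day 29 cannot be managed, so Day 30-31 last doses should be a minority. The number of short visit days in the table says nothing about how often they would be used.
- The 20% figure needs the latest scan, the earliest visit and the longest half-life together. At 20 h, five half-lives are 5 x 20 = 100 h, and a Day 36 visit after a Day 31 dose (120 h) already exceeds that.
- The last-dose + 7 period in 11.4.3 is an analysis definition, not a visit rule; 4.4 and 6.2.1 are what set the length of follow-up. The advice in 10.1.4 that begins "Approximately seven days after the last study drug intake, the investigator will prescribe if needed anti-anginal drugs" already counts from the last intake and does not conflict with Visit 6.

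There is partial mitigation. Section 10.4.3 follows known AEs to recovery or stabilisation, beyond the last visit if necessary, and 10.4.4 takes in related serious events that come to light later. Neither schedules a measurement or detects a new non-serious event between Visit 6 and last dose + 7 days.

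**Conclusion.** The inconsistency is real and modest. As written, a compliant completer can have 3 to 6 days of post-dose observation against a stated week. After a Day 31 last dose, up to 4 of the 7 days are unobserved, and only a Day 38 visit covers them all. The day counts rest on the protocol's own dates alone. The residual-drug figures rest on the 20 to 31 h range and simple exponential decay.

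The consequence is incomplete capture of new non-serious AEs and of scheduled blood pressure and laboratory checks. Two stronger inferences are not supported:
- **Bias between arms.** The schedule is the same in both arms, and the safety analysis is descriptive without testing.
- **Final blood pressure and renal results as intended drug-free values.** Section 10.1.5 lists the tests without giving that purpose, and 4.4 speaks of collecting AEs during washout, not after it.

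The practical reach is also limited: SAP section 1.2 reports that only 10 patients were randomized before the sponsor stopped the study.

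**What to change.** Reconcile 1.3.1, 1.3.2, 6.2.1, 9.2.1 and 10.1.5 with the synopsis, 4.4 and 11.4.3:
- For patients who complete treatment, time Visit 6 from the last study drug intake, using the documents' own 7 days and a window that does not open earlier. The earliest visit would be Day 36, 37 or 38 for a last dose on Day 29, 30 or 31.
- End AE collection at that visit or at Day 36, whichever is later. Without this clause, a rule of last dose + 7 would close collection early for patients who stop prematurely: someone stopping on Day 10 would close at Day 17, against Day 36 in 9.2.1 and the continued observation required by 10.4.3.
- Adjust the total duration and its tolerance in 6.2.1 and the synopsis to match.

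**Cost.** Protocol wording and less scheduling freedom; no added visit or test. If the window were 0 to +2 days, a visit that could have been on Day 34 after a Day 31 dose would move to Days 38-40, which is 38 - 34 = 4 to 40 - 34 = 6 days later.
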